6 STUDY RISKS

6.1 Discomfort during MBI

An MBI exam involves an intravenous injection in the arm, which may cause minor discomfort. Following each injection, the subject is required to sit on a chair for ~40 minutes for the MBI with either breast placed in light compression during the image acquisitions. This procedure should cause little to no discomfort to the subject.

6.2 Tc-99m sestamibi

Tc-99m sestamibi is an FDA-approved drug with an excellent safety profile. This drug has been safely used in clinical practice for over 30 years. Very rarely, patients receiving sestamibi experience mild symptoms such as flushing, a rash, or a brief metallic taste after injection.

6.3 Radiation

The radiation dose from a total administered dose of 8 mCi Tc-99m sestamibi has an effective (whole-body) dose of \sim 2.1 mSv. Subjects will undergo two MBI examinations for a total effective dose of about 4.2 mSv. This radiation dose has a very low risk of harmful effects. Pregnant women and women who are nursing will not be permitted to participate in this study.

6.4 Incidental findings on MBI

Based on prior studies of screening MBI in women with dense breasts, we expect that about 5% of study participants will have an abnormality found on the MBI test. Finding an abnormality on the study testing can be emotionally distressing to participants. Participants with concerning findings on MBI will be recommended to return for additional diagnostic

workup, as per routine clinical standard of care. Participants will be informed that any additional testing beyond the MBI test is not part of this research study and financial costs will need to be covered by the patient and their insurance.

6.5 Risks of Tamoxifen

Tamoxifen has been used for over 40 years to treat hormone-receptor positive breast cancer. Side effects of tamoxifen taken at the standard 20 mg dose, ranging from mild to serious, have been reported. We expect side effects at the 5 mg or 10 mg dose to occur less frequently, if at all, especially over the short time frame of 30 days.

In patients taking standard 20 mg dose tamoxifen, vasomotor symptoms (hot flashes and night sweats) and vaginal discharge are the most likely side effects. However, in studies of women taking low-dose (5 mg or 10 mg) tamoxifen, hot flashes and vaginal discharge were not increased compared to women taking placebo.

Among women taking 20 mg tamoxifen for 5 years, there is a small increased risk of uterine cancer, abnormal blood clots, or vision changes. Other less serious side effects reported from 20 mg tamoxifen treatment include changes in menstrual cycle (among premenopausal women), weight gain, depression, insomnia, and urinary incontinence. These side effects are not expected to occur for short-term, low-dose tamoxifen used in this study.

Tamoxifen can cause birth defects. Participants who can become pregnant will undergo a pregnancy test prior to MBI, which must be negative. Participants will be instructed to avoid pregnancy during the study and for at least 2 months after study participation ends, by abstinence, barrier method, or nonhormonal contraception. If a participant should become pregnant, she will be instructed to stop using tamoxifen immediately.

7 ADVERSE EVENTS

Participants will be asked to report any adverse events or side effects, should they occur, by contacting study staff. At approximately days 5 and 20 of the tamoxifen intervention, the study coordinator will contact participants by phone to assess medication compliance and inquire about any adverse events. Adverse events will also be assessed at the study closeout during Study Visit 2. The duration and severity of adverse events will be recorded.

Although we do not expect serious side effects to occur with 5 mg tamoxifen over a 30-day period, patients will be advised to stop taking tamoxifen medication immediately if any of the following should occur:

- vision problems
- loss of appetite
- yellowing of skin or eyes
- unusual bruising or bleeding
- fever
- blisters

- rash
- swelling of eyes, face, lips, tongue, throat, hands, arms, feet, ankles, or lower legs
- thirst
- muscle weakness
- restlessness
- vaginal bleeding or spotting

8 REMUNERATION

Participants will receive a total of \$200 to compensate for their time spent in the study. If participants start the study but do not finish, they will receive part of the money. The breakdown of remuneration payments will be as follows:

Study Visit 1: \$50

Completion of 30 days tamoxifen: \$100

Study Visit 2: \$50

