4.1 Inclusion Criteria

The following are requirements for entry into the study:

- 1) Female, age 40 or older at the time of enrollment
- 2) Most recent MBI examination, performed within 3 years of enrollment, showed moderate or marked background parenchymal uptake
- 3) Mammogram performed within 24 months prior to enrollment that is available for comparison
- 4) Willing and able to return for MBI following 30 days of low-dose tamoxifen
- 5) If able to become pregnant
 - a. Negative pregnancy test within 48 hours prior to study MBI exam(s)
 - b. Agrees to avoid pregnancy during the study and for at least 2 months after study participation ends, by abstinence, barrier method, or nonhormonal contraception.
- 6) Understands and signs the consent form

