4.2 Exclusion Criteria

Subjects will be excluded if any of the following characteristics are present:

- 1) Evidence of suspected breast disease as defined by positive findings or recommendation for short-interval follow-up on most recent breast imaging (including mammography, MBI, MRI, ultrasound, etc.) not yet resolved prior to enrollment
- 2) Breast biopsy or breast surgery performed within 6 months prior to enrollment
- 3) Bilateral breast implants or status post-bilateral prophylactic mastectomy
- 4) Pregnant or lactating
- 5) Current or recent use (within 6 months prior to enrollment) of any of the following drugs:
 - a. Systemic hormonal therapy (oral or transdermal patch formulations)
 - b. Hormonal contraception (oral, transdermal, implanted, or injected formulations not allowed, however hormonal IUDs are acceptable)
 - c. Selective estrogen receptor modulators (tamoxifen, raloxifene, or toremifene)
 - d. Aromatase inhibitors (anastrazole, letrozole, or exemestane)
 - e. GnRH analogs
 - f. Prolactin inhibitors
 - g. Androgens or antiandrogens

- h. Anticoagulants or "blood thinners" (warfarin, heparin, rivaroxaban and other novel anticoagulants)
- i. Drugs known to be strong inhibitors of CYP2D6, the major P450 enzyme that metabolizes tamoxifen, including:
 - bupropion (Wellbutrin)
 - fluoxetine (Prozac)
 - paroxetine (Paxil)
 - quinidine (Quinidex)
- 6) Personal history of any type of malignancy, with the exclusion of non-melanoma skin cancer, diagnosed prior to enrollment
- 7) Personal history or strong family history of blood clots in legs or lungs (also known as deep vein thrombosis or pulmonary embolism)
- 8) Personal history of transient ischemic attack (TIA) or cerebrovascular accident (CVA)
- 9) Active proliferative disorders of the endometrium such as atypical hyperplasia, history of active endometriosis, unresected polyps
- 10) Any type of retinal disorders or severe cataract
- 11) Current smoker
- 12) Known carrier of BRCA1 or BRCA2 genetic mutation or known DNA repair defect.
- 13) Blood pressure above 140/90

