9 SAMPLE SIZE CONSIDERATIONS

There have yet to be any studies examining BPU response to tamoxifen. Thus, this study is a pilot design that will aim to enroll 30 patients who complete pre- and post-tamoxifen MBI. A sample size of 30 will have 80% power to detect a means change of 1 BPU quantitative unit (e.g. overall mean of 4.5 pre low-dose tamoxifen intervention, and post tamoxifen mean of 3.5), assuming a standard deviation of differences of 1.89 (effect size = 0.53), using a paired t-test with an α =0.05 two-sided significance level.

Allowing for potential study withdrawals, we will allow for a total of 50 patients to begin the low-dose tamoxifen intervention. In addition, women who are invited to participate may not have persistent BPU on their MBI performed at Study Visit 1. Prior pilot data showed that approximately half of women with prior high BPU had persistent high BPU on a current MBI. Therefore, up to 100 women will be screened with MBI to assess potential enrollment in the low-dose tamoxifen intervention. We will aim to balance enrollment of premenopausal and postmenopausal subjects.

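### The Section 7 stop list does not exempt an expected period; read literally, it would cut the 30-day course short in most regularly cycling women

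*Combined protocol and SAP*

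**What the plan says.** Section 7 (Adverse Events) states that "patients will be advised to stop taking tamoxifen medication immediately if any of the following should occur", and the list closes with "vaginal bleeding or spotting". That item has no qualifier. An earlier item in the same list, on bruising and bleeding in general, is limited to what is unusual. No section exempts an expected period.

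Other sections bear on the point:

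- **Who is enrolled.** Section 4.1 admits women from age 40 with no menopausal restriction, and Section 9 adds: "We will aim to balance enrollment of premenopausal and postmenopausal subjects". Exclusion 5b in Section 4.2 rules out hormonal contraception in the six months before enrollment, except hormonal IUDs.
- **What exposure is intended.** Section 2 sets the objective in terms of 30 days at 5 mg or 10 mg. Inclusion criterion 4 asks that a woman be "Willing and able to return for MBI following 30 days of low-dose tamoxifen". Section 8 attaches $100 of the $200 payment to "Completion of 30 days tamoxifen".
- **What happens on an early stop.** Section 5.6 asks women who choose to stop before day 30 to come back for the second MBI at that point.
- **Staff contact.** Section 7: "At approximately days 5 and 20 of the tamoxifen intervention, the study coordinator will contact participants by phone", to ask about compliance and adverse events.
- **Menstrual effects.** Section 6.5 places changes in the menstrual cycle among the less serious side effects of the 20 mg dose and does not expect them here.

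**The concern.** A 30-day course is about as long as one menstrual cycle. A stop rule triggered by any vaginal bleeding will therefore be met, in the ordinary course of events, by most women who are still cycling. The list has other unqualified items, such as thirst and fever. A period differs from these because it can be predicted to fall within the course and because it occurs in one menopausal group only.

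A woman taking capsules at home who follows the wording would stop at her next period. Section 5.6 would then bring her second MBI forward. Some premenopausal women could thus receive a shorter and variable course in place of the 30 days named in the objective, while postmenopausal women would not. Section 1.2 reports that BPU is associated with menopausal status, so a shortening confined to one menopausal group would make the before-after change harder to read. A woman who obeyed the instruction might also forgo some or all of the payment for completing the drug.

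**Working it through.** **The plan's own figure.** The plan gives no figure for early stopping. Its one design calculation, in Section 9, is 80% power with 30 women, a mean change of 1 unit, an SD of differences of 1.89 and a two-sided paired t-test at 0.05. With 29 degrees of freedom and noncentrality √30 × 1/1.89 = 2.90, the power is 0.80, which reproduces the stated value. This point does not dispute that figure.

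**Inputs from the protocol.** Course of 30 days (Section 5.6); calls at about days 5 and 20 (Section 7).

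**Assumptions, since the protocol gives no cycle data.** Regular cycles of length L days, with 24 to 35 as the main range and 45 and 60 shown for contrast. Drug starts at a random point in the cycle. Hormonal IUD users are not counted. Bleeding already under way on day 1 is ignored.

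**Formulas.** Time T from first dose to the next period is then uniform on (0, L).

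- Period starts within the course: P(T ≤ 30) = min(1, 30/L)
- Period starts before a call on day d: P(T ≤ d) = d/L
- Mean days on drug, if she stops at the period and does not restart: E[min(T, 30)] = L/2 for L ≤ 30, and 30 − 450/L for L > 30

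**Results.**

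| L (days) | Period within 30 days | Before day 5 call | Before day 20 call | Still to come at day 5 | Mean days on drug if stopped literally |
|---|---|---|---|---|---|
| 24 | 100% | 21% | 83% | 79% | 12.0 |
| 28 | 100% | 18% | 71% | 82% | 14.0 |
| 30 | 100% | 17% | 67% | 83% | 15.0 |
| 35 | 86% | 14% | 57% | 86% | 17.1 |
| 45 | 67% | 11% | 44% | 89% | 20.0 |
| 60 | 50% | 8% | 33% | 92% | 22.5 |

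For example, at L = 35: 30/35 = 0.86, 5/35 = 0.14, 20/35 = 0.57, and 30 − 450/35 = 17.1 days.

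A simulation with random start phases agreed with the first and last of these formulas for cycles of 21 to 45 days. Counting an assumed 5-day bleed already in progress at the first dose raises the proportion meeting the rule to 100% for every cycle length tested up to 35 days, so leaving it out understates the result.

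**What cannot be computed.** The protocol does not say how many participants cycle regularly, how many would apply the wording literally, or how BPU change depends on days of drug. No count of affected women, bias or loss of power follows from these figures.

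**The case against.** The strongest reply is that nobody would read the item this way. The list is introduced as possible side effects, and a normal period is not one. Section 6.5 speaks of changes in the cycle, not of the cycle itself. The trial deliberately recruits premenopausal women and pays for a full course, which a literal reading would defeat. This stands as evidence of intent, and abnormal bleeding is probably what was meant. It does not remove the problem: the list tells a woman at home to stop immediately, none of those sections tells her that a period does not count, and the same list does limit general bleeding to what is unusual.

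Second, Section 7 describes advice, and the wording given to participants was not available. It may already make the exception. This also stands and limits how firmly the point can be put.

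Third, staff can correct a misreading at the in-person enrollment visit or by phone. The day 5 call would precede the period in about 79% to 86% of regularly cycling women, so it is a real safeguard if menses are raised. The protocol does not say that they are, and the day 20 call would come too late for most.

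Fourth, a woman who paused could restart after contacting staff. Nothing forbids this, but nothing provides for it either, and Section 5.6 brings the second MBI forward for women who choose to stop early.

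Fifth, a broad stop rule is a defensible caution in healthy women taking a drug with a uterine risk. That is a reason to keep abnormal bleeding on the list, not to leave an expected period on it.

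**Conclusion.** The concern holds, as a minor point. As written, the item has no exemption for an expected period. Followed literally, it would end the course early in about 86% to 100% of women with regular 24- to 35-day cycles, with about 12 to 17 days of drug on average.

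These figures rest on the assumed cycle lengths, a random start within the cycle, literal compliance and no restart. They describe what the rule would do if followed, and do not predict what participants will do. Confidence is medium, because the intent is probably narrower than the wording and the participant materials could not be checked. No effect on BPU change or on power is claimed.

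**What to change.** Replace the last item of the Section 7 list with wording such as: *any postmenopausal bleeding or, in premenopausal women, unexpected, intermenstrual or unusually heavy vaginal bleeding or spotting; an expected period is not a reason to stop; if unsure, call study staff.*

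Use the same wording in the participant instructions and in the day 5 and day 20 calls. The written instruction matters most for the roughly 14% to 21% whose period would start before the first call. Add the start date of any bleeding to the existing Drug Diary.

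The cost is one reworded item, matching instructions and call wording, and one diary field, with no added visits, tests or patients. The downside is that women with irregular cycles must judge whether bleeding was expected; the line about calling when unsure covers this. Bleeding outside an expected period remains a reason to stop.

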5.6 Low-dose tamoxifen intervention

Subjects will be enrolled to one of two arms of the study. The study arms will be identical, except for the dose of tamoxifen. For Arm 1, the dose of tamoxifen will be 5 mg per day for 30 days. For Arm 2, the dose of tamoxifen will be 10 mg per day for 30 days.

Participants will receive a prescription for tamoxifen. A physician co-principal investigator will order participant prescriptions, which will be filled through the Mayo Clinic Outpatient Research Pharmacy. For subjects in Arm 1, the research pharmacy will perform splitting of the standard tamoxifen tablets (available in either 10 mg or 20 mg doses) and over-encapsulation to arrive at 5 mg tablets.

Participant instructions for the tamoxifen medication will be as follows:

- Take one capsule per day for 30 days
- Take each dose at approximately the same time each day
- Capsules should be taken with water or a non-alcoholic beverage. Capsules can be taken with or without food.
- If you miss a dose, take the missed dose as soon as you remember it. However, if it is almost time for the next dose, skip the missed dose and continue your regular dosing schedule. Do not take a double dose to make up for a missed one.

Participants will also be given a "Drug Diary" log and asked to make notes of when each dose is taken and to record any symptoms experienced. Participants will be asked to return

Drug Diary logs and pill bottles at the Study Visit 2. Any remaining pills will be returned to the Outpatient Research Pharmacy for disposal.

Participants will be advised that they may elect to stop the tamoxifen medication at any time, should they experience unwanted side effects. Patients will be asked to contact study staff if they do choose to stop. Patients who start tamoxifen but choose to stop earlier than 30 days will be asked to return for their post-tamoxifen MBI test (Study Visit 2) at that time.

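### Half of the payment depends on completing 30 days of tamoxifen, with no stated exception for a woman who stops as Sections 5.6, 6.5 or 7 allow, instruct or advise

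*Combined protocol and SAP*

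**What the plan says.** Section 8 (Remuneration) states the purpose of the payment: "Participants will receive a total of \$200 to compensate for their time spent in the study". It lists three parts: "Study Visit 1: \$50", 100 dollars for "Completion of 30 days tamoxifen", and "Study Visit 2: \$50". For women who do not complete the study it says only: "If participants start the study but do not finish, they will receive part of the money". It gives no formula for the part payment, and no exception for a woman who stops on the protocol's own advice.

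Three other sections deal with stopping:

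- Section 5.6 tells participants that "they may elect to stop the tamoxifen medication at any time, should they experience unwanted side effects". It asks early stoppers to tell the staff and to come back for the second MBI when they stop.
- Section 6.5 says that a participant who becomes pregnant will be instructed to stop immediately.
- Section 7 says that "patients will be advised to stop taking tamoxifen medication immediately if any of the following should occur", followed by 12 symptoms.

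Information on symptoms comes from the participant: her own contact with staff, phone calls at about days 5 and 20, the Drug Diary, and the close-out at Study Visit 2. Compliance is asked about in the same calls and recorded in the diary. Pill bottles are also returned at Study Visit 2.

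**The concern.** One part of the plan gives a woman advice about when to stop, and another takes money from her, or appears to, if she follows it. Several of the 12 symptoms, such as thirst, restlessness and loss of appetite, are for the woman herself to notice and judge. A financial reason to overlook one of them is therefore a reason not to follow Section 7.

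The second stake is the data. A woman who has stopped, or who has a symptom that should make her stop, has a reason not to say so. This is a pilot with no earlier study of BPU response to tamoxifen (Section 9). If BPU changes little, the investigators will want to know whether the drug was taken. Section 5.6 brings known early stoppers back for MBI at the time they stop. A woman who stopped after day 10 and did not say so would instead be scanned at day 30, some 20 days after her last dose, and counted as having had the full course.

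**Working it through.** **Inputs (Section 8).** Visit 1: 50 dollars. Completion of tamoxifen: 100 dollars. Visit 2: 50 dollars. Stated total: 200 dollars.

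**The plan's own figure.** 50 + 100 + 50 = 200, which matches the stated total.

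**Share tied to taking the drug.** 100 / 200 = 50%.

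**What an early stopper receives.** Because Section 5.6 asks her back for the second MBI, the Visit 2 payment remains open to her. Two readings of the part-payment sentence are possible.

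- *Literal:* the 100 dollars is earned only by completion. She receives 50 + 0 + 50 = 100 dollars.
- *Prorated by day (an assumption; Section 8 does not say so):* after d days she receives 50 + 100 × d/30 + 50, a loss of 100 × (30 − d)/30.

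| Woman attends both visits and | Received, literal | Loss, literal | Received, prorated | Loss, prorated |
|---|---|---|---|---|
| completes 30 days | 200 | 0 | 200 | 0 |
| stops after day 5 | 100 | 100 | 116.67 | 83.33 |
| stops after day 15 | 100 | 100 | 150 | 50 |
| stops after day 25 | 100 | 100 | 183.33 | 16.67 |

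Stopping costs money under both readings. The loss would be zero only if some text outside Section 8 preserved the full 100 dollars.

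**Setting the sections side by side.** Section 8 calls the payment compensation for time. A woman who stops early and attends both visits gives the same visit time as one who completes, yet receives less. Completion is also not defined. Section 5.6 tells women to skip a missed dose when the next one is almost due, so a woman who follows the instructions exactly may take fewer than 30 capsules. Section 8 does not say whether she has completed.

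**What can be checked independently.** Returned bottles allow leftover capsules to be counted, which is a partial check on compliance: an absent capsule is not proof of a dose taken. The documents describe no comparable independent check on symptoms.

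**Number affected.** Section 9 aims for 30 women with both MBIs and allows up to 50 to begin tamoxifen. It does not say how many will stop the drug early.

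**The case against.** The best defence is that staged payment is ordinary, that the woman is told she is free to stop, and that an early stopper can still earn 100 dollars from the two visits. The 100 dollars may be meant to cover a month of capsules, diary entries and calls. The consent form is not in the text reviewed and may set out proration or an exception. All of this softens the point. It does not remove it, because Section 8 as written contains no exception.

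Four stronger readings are tempting, and the documents do not support them.

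- *A woman loses money by reporting a symptom.* The payment depends on completion, not on being symptom-free. Reporting costs nothing unless it leads to stopping. Hot flashes, night sweats and vaginal discharge, which Section 6.5 names as the most likely effects at the standard dose, are not on the Section 7 list.
- *The participant is the only source of the data.* This is close to true for symptoms. It is not true for compliance, because bottles are returned.
- *Adherence and symptom counts are biased.* The documents show an incentive, not misreporting. No planned comparison uses self-reported adherence. BPU is read blinded to the order of the studies (Section 5.5) and measured as a count ratio (Section 5.7), so any effect is on interpretation and on the description of tolerability.
- *Up to 20 of 50 women would be affected, at a cost of 2,000 dollars.* The difference 50 − 30 = 20 allows for women without both MBIs. Early stoppers who return for MBI can be among the 30, so 20 is not a count of women who stop the drug.

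**Conclusion.** The concern holds as a conflict between sections. Half of the payment (100 of 200 dollars) is tied to taking tamoxifen for 30 days, with no stated exception for stopping under Sections 5.6, 6.5 or 7. A woman who stops as advised and attends both visits loses 100 dollars on the literal reading. If the payment is prorated, she loses less, for example 83.33 dollars after day 5 or 16.67 after day 25. This is a financial incentive against the plan's own stop advice, and it may discourage disclosure of listed symptoms or of stopping.

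The conclusion assumes that nothing outside Section 8, in particular the consent form, restores the payment. The extent of any misreporting is unknown. The point is minor for the planned analysis of BPU and carries more weight for safety and for the exposure record. It implies no view on the doses or on the list of symptoms.

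**What to change.** Reconcile Section 8 with Sections 5.6, 6.5 and 7. Pay the 100 dollars for returning the Drug Diary and pill bottle and attending close-out at Study Visit 2, whatever number of days was taken. This keeps an incentive, but attaches it to returning data. At the least, state in Section 8 and in the consent form that stopping under those sections does not forfeit the 100 dollars. If the consent form already says so, copy the rule into Section 8.

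The cost is a change to payment and consent wording, and up to 100 dollars for each early stopper who returns. The documents do not give that number. The absolute ceiling, if all 50 starters stopped early and all returned, is 50 × 100 = 5,000 dollars. The downside is a slightly weaker incentive to complete 30 days. Doses, stop advice, visits, sample size and analysis are unchanged.
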